13.3.2. Overdose, Abuse, Misuse, Medication Errors, and Occupational Exposure

All incidences of overdose, abuse, misuse, medication errors, and occupational exposure are required to be reported to Karyopharm Pharmacovigilance on an SAE report form, emailed to [contact], regardless of whether or not there is an associated AE or SAE.

13.3.2.1. Overdose

An overdose is a deliberate or accidental administration of any study treatment to a study patient, at a dose greater than that which was assigned to that patient per the study protocol. If an overdose occurs, the Investigator and Karyopharm should be notified immediately, and the patient should be observed closely for AEs. Resulting symptoms should be treated, as appropriate, and the incident of overdose and related AEs and/or treatment should be documented in the patient's medical record and in the eCRF. Overdose is to be reported on an SAE report form to Karyopharm Pharmacovigilance regardless of whether or not an AE or SAE has occurred due to the overdose. If the overdose is associated with an SAE, the SAE report form must be submitted to Karyopharm Pharmacovigilance within 24 hours of awareness. If there is no AE or SAE, the report must be submitted within 24 hours of awareness.

As selinexor is metabolized by GSH conjugation, it is possible, but not demonstrated, that hepatic GSH depletion might occur in case of extreme overdose. Therefore, in overdose cases, if patients develop liver function test abnormalities, supportive measures such as SAM or other drugs that can replace GSH might be considered as part of the overall management plan.

13.3.2.2. Abuse, Misuse, or Medication Error

Abuse is the persistent or sporadic, intentional excessive use of the study treatment which is accompanied by harmful physical or psychological effects.

A medication error is any preventable incident that may cause or lead to inappropriate study treatment use or patient harm while the study treatment is in the control of the health care professionals or patients. Such incident may be due to health care professional practice, product labeling, packaging and preparation, procedures for administration, and systems, including the following: prescribing, order communication, nomenclature, compounding, dispensing, distribution, administration, education, monitoring, and use.

All occurrences of abuse, misuse, or medication error with any study treatment are to be reported on an SAE report form to Karyopharm Pharmacovigilance regardless of whether or not an AE or SAE has occurred due to the abuse, misuse, or medication error. If the abuse, misuse, or medication error is associated with an SAE, the SAE report form must be submitted to Karyopharm Pharmacovigilance within 24 hours of awareness. If there is no AE or SAE, the report must be submitted within 24 hours of awareness.

13.3.2.3. Occupational Exposure

Occupational exposure is the exposure to a study treatment as a result of one's professional or non-professional occupation.

All occurrences of occupational exposure with any study treatment are to be reported on an SAE report form to Karyopharm Pharmacovigilance regardless of whether or not an AE or SAE has occurred due to the occupational exposure. If the occupational exposure is associated with an SAE, the SAE report form must be submitted to Karyopharm Pharmacovigilance within 24 hours of awareness. If there is no AE or SAE, the report must be submitted within 24 hours of awareness.

14. STATISTICAL METHODS

A statistical analysis plan (SAP) will be finalized prior to database lock. Any deviation from the statistical plan will be described in the final report.

14.1. General Considerations

This is a multicenter randomized double-blind Phase 2-3 study of the SINE selinexor given orally in patients with advanced unresectable liposarcoma.

Enrollment in Phase 2 has been completed and the preplanned analysis of PFS (after 40 PFS events were observed) was performed. Details are provided in Section [14.1.1.1](#).

There was no break between Phase 2 and Phase 3 enrollment.

In Phase 3, patients will be randomized in a 2:1 fashion to receive selinexor (60 mg) or placebo. Randomization details are provided in Section [7.7](#).

Patients in the placebo arm who have PD while they are receiving blinded study treatment will be allowed to cross over to open-label selinexor (see Section [7.2.1](#)).

Patients who are on blinded study treatment at the time of the primary PFS analysis at the end of Phase 3 may proceed as follows:

- Patients in the placebo arm may cross over to open-label selinexor.
- Patients in the selinexor arm will continue selinexor but as open-label treatment.

Tabulations will be produced for appropriate demographic, baseline, efficacy, and safety parameters. For categorical variables, summary tabulations of the number and percentage of patients within each category (with a category for missing data) of the parameter will be presented, as well as two-sided 95% CIs, unless otherwise stated. For continuous variables, the number of patients, mean, median, standard deviation, minimum, and maximum values will be presented. Time-to-event data will be summarized with Kaplan-Meier methodology using 25th, 50th (median), and 75th percentiles with associated 2-sided 95% CIs as well as percentage of censored observations.

14.1.1. Determination of Sample Size

14.1.1.1. Determination of Sample Size for Phase 2

Enrollment in Phase 2 has been completed.

Fifty-seven patients were randomized to selinexor or placebo in a 1:1 allocation. Randomization details are provided in Section [7.7](#).

[figure not shown]
The preplanned analysis of PFS (after 40 PFS events were observed) was performed and served as a guideline to inform the final design of the Phase 3 portion of the study.

A summary of the preliminary efficacy results for Phase 2 is provided in Section [4.3.2](#).

14.1.1.2. Determination of Sample Size for Phase 3

[figure not shown]
Per protocol, the Phase 3 sample size was re-evaluated based on the Phase 2 results. Sample size calculations were conducted under the following assumptions:

CCI

Based on these assumptions, approximately 277 eligible patients will be randomized 2:1 to receive either selinexor (60 mg twice weekly) or placebo, respectively in a blinded manner to observe 209 PFS events. Sample size may be re-estimated based on the interim analysis (see Section 14.1.1.2.1).

CCI

[figure not shown]

14.1.1.2.1. Phase 3 Interim Analysis After 105 PFS Events

The interim analysis was conducted at 108 PFS events and the results were reviewed by the DSMB on September 25, 2019. The purpose of this interim analysis was for sample size re-estimation with an early stopping boundary for efficacy.

An external, unblinded statistician calculated and presented to DSMB members

CCI

Based on the safety and efficacy data, the DSMB recommendation was continuation of the study with no change to safety monitoring and no sample size adjustment.

All sample size calculations were conducted using EAST Version 6.4 or higher ([East 2016](#)).

14.1.2. Blinding and Randomization

Study treatment will be administered in a blinded manner. Randomization will be performed across study sites within the stratification factors, in order to maintain the required 1:1 (selinexor:placebo in Phase 2) or 2:1 (selinexor:placebo in Phase 3) randomization. Randomization will be performed by a centralized system after confirmation of patient eligibility by the Sponsor (see Section [7.6](#) and Section [7.7](#)).

14.2. Analysis Population

14.2.1. Intent-to-Treat Population

The intent-to-treat (ITT) population will consist of all patients who are randomized to study treatment in Phase 3. This population will be used for primary analyses of efficacy. Patients will be analyzed in the treatment arm to which they were randomized.

14.2.2. Per-Protocol Population

The per-protocol (PP) population will consist of all patients in the ITT population who have no major protocol violations, including mis-randomizations, that would compromise the assessment of efficacy; this would include receipt of sufficient study treatment (80% compliance or more). Major violations will be determined independently of knowledge of response to study treatment. This population will be used for supportive inferences concerning efficacy. Patients will be analyzed according to the treatment actually received.

14.2.3. Safety Population

The safety population will consist of all patients who have received any amount of study treatment. Patients will be analyzed according to the treatment actually received.

14.3. Data Analysis and Presentation

Summary tabulations will be provided for disposition, demographic, baseline, efficacy, and safety data as noted in the following sections. All data collected on the eCRF will be provided in by-patient data listings.

14.3.1. Disposition of Patients

A tabulation of patient disposition will be presented including the number in each analysis population, the number in each analysis population, the number censored at each of the PFS and OS analyses, the number lost to follow-up, the number that withdrew, and reason(s) for withdrawal.

A by-patient listing of patient disposition information including the reason for study withdrawal, where applicable, will be presented.

14.3.2. Demographic Characteristics

Demographic characteristics will be summarized by treatment arm, as well as overall, and will include gender, race, ethnicity (Hispanic origin), and age at time of consent. For gender, race, and Hispanic or Latino origin, the summary statistics will be the number and percentage of patients within each category. The categories for race will be those recorded in the database. For age at time of consent, the mean, median, minimum, maximum, and standard deviation will be provided for each arm and the total sample. No formal hypothesis testing of treatment differences will be performed.

14.3.3. Baseline Characteristics and Medical History

Baseline characteristics include ECOG performance status, duration from initial diagnosis, response to previous therapy, types of prior therapy, and number of prior therapies. Baseline data will be summarized for each treatment group using summary statistics; no formal hypothesis testing of treatment differences will be performed.

Medical history and physical examination results at baseline will be tabulated by treatment.

14.3.4. Efficacy Analysis

Disease assessments at the date of surgical or radiotherapy intervention may be censored in patients receiving such care, since these patients are receiving non-protocol specified therapy (ie, intervention), which may impact endpoint(s).

Based on the preplanned analysis of PFS by WHO and RECIST v. 1.1 Criteria in the Phase 2 portion of the study, the response criteria for the primary analysis (PFS) were changed from WHO to RECIST v. 1.1 Criteria in Version 4.0 of the protocol. Consequently, data from the Phase 2 portion of the study will be excluded from the final efficacy analysis in order to maintain statistical integrity and preserve overall Type I error rate.

14.3.4.1. Efficacy Analysis for Phase 2

All Phase 2 analyses will be conducted among Phase 2 patients only.

Phase 2 Primary Endpoint Analysis:

The preplanned analysis of PFS after 40 PFS events was conducted with an 11 August 2017 data cut with 49 eligible patients whose treatment assignments were available. Patients were analyzed in the treatment arm to which they were randomized. The preplanned PFS analysis was conducted by both WHO and RECIST v. 1.1 Criteria and served as a guideline to inform the final design of the Phase 3 portion of the study. See Section [4.3.2](#) for a summary of the preliminary data.

The primary endpoint PFS for Phase 2 is defined as the time from date of randomization until the first date of PD, per RECIST v. 1.1, or death due to any cause. Evaluation of the radiographic data for the PFS primary endpoint will be based on data from a scan review by the independent central reader.

The formal primary Phase 2 PFS analysis will be performed on all 56 eligible patients randomized to study treatment in Phase 2 when their treatment assignments are unblinded. Patients will be analyzed in the treatment arm to which they are randomized.

PFS data will be summarized with Kaplan-Meier methodology using 25th, 50th (median), and 75th percentiles with associated 2-sided 95% CIs, as well as percentage of censored observations. The stratified log-rank test will be used to compare the PFS distributions between treatment arms.

Phase 2 Secondary Endpoint Analysis

Secondary efficacy variables will include the following, according to the definitions described in the objectives and study endpoints:

- TTP on study treatment compared with TTP on the patient's last prior systemic therapy
- ORR
- DOR
- Tumor glucose metabolism, density, and size using FDG-PET and CT (diagnostic) after 6 weeks of treatment.

Secondary time-to-event endpoints will be analyzed using the stratified log-rank test as described above.

CCI

Phase 2 Sample Size Calculation and Statistical Power

Enrollment in Phase 2 has been completed. Details are provided in Section [14.1.1.1](#).

14.3.4.2. Efficacy Analysis for Phase 3

The final efficacy analysis will be conducted among Phase 3 patients only.

Stratified log-rank tests will be used to compare the distributions of time-to-event endpoints (PFS, OS, DOR, TTP) between the two arms using a 1-sided test and alpha=0.025 level of significance, and to estimate event free rate at various time points (eg, 1- year rate, 2-year rate, etc.) along with 95% CIs. Stratification factors for the stratified log-rank test are those that were used for randomization. The Cui, Hung, and Wang (CHW) method ([Cui 1999](#)) will be used to account for interim testing and possible sample-size re-estimation to preserve the overall Type I error rate.

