7.5.2.2. Secondary Efficacy Endpoints

- TTP, defined as the time from randomization to date of PD or death due to disease progression, whichever is earlier, per RECIST v. 1.1. Patients who remain progression free (whether they withdrew from the study or reached their maximum follow-up) will be censored at the date of their last disease assessment.
- ORR, defined as the proportion of patients who achieve complete response (CR) or partial response (PR), per RECIST v. 1.1.
- DOR, defined as the time from first occurrence of CR or PR until the first date of PD per RECIST v. 1.1 or death.
- Tumor glucose metabolism, density, and size using FDG-PET (Phase 2 only) and CT (diagnostic) after 6 weeks of treatment.
- PFS according to the Investigator, defined as the time from date of randomization until the first date of PD, per RECIST v. 1.1, or death due to any cause as defined by the Investigator based on clinical and/or radiologic criteria.
- Time to next treatment (TTNT), defined as the duration of time from randomization to the date of the next anti-cancer therapy.

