7.7. Randomization to Blinded Study Treatment

In Phase 2, patients were randomized to either selinexor (60 mg) or placebo in a 1:1 ratio. Randomization was stratified based on the following stratification factors for patients enrolled under protocol Versions ≤ 4 : the number of prior systemic therapies (1 versus ≥ 2) and prior eribulin use (prior eribulin versus no prior eribulin).

In Phase 3, patients will be randomized to selinexor or placebo in a 2:1 ratio. Randomization will be stratified based on (a) prior eribulin use (prior eribulin versus no prior eribulin), (b) prior trabectedin (Yondelis[®]) use (prior trabectedin versus no prior trabectedin), and (c) the number of prior systemic therapies excluding eribulin and trabectedin (2 versus ≥ 3).

Specifically, randomization will be performed within each of the following 8 strata:

1. ≤ 2 prior systemic therapies without prior eribulin use or prior trabectedin use

2. ≤ 2 prior systemic therapies without prior eribulin use but with prior trabectedin use
3. ≤ 2 prior systemic therapies with prior eribulin use but without prior trabectedin use
4. ≤ 2 prior systemic therapies with both prior eribulin use and prior trabectedin use
5. ≥ 3 prior systemic therapies without prior eribulin use or prior trabectedin use
6. ≥ 3 prior systemic therapies without prior eribulin use but with prior trabectedin use
7. ≥ 3 prior systemic therapies with prior eribulin use but without prior trabectedin use
8. ≥ 3 prior systemic therapies with both prior eribulin use and prior trabectedin use

Randomization will be performed by a centralized system after confirmation of patient eligibility by the Sponsor (see Section [7.7](#)).

Study treatment will be administered in a double-blinded manner until the analysis of the primary PFS endpoint at the end of Phase 3, with the following exceptions: 1) patients in the placebo arm who have PD while they are receiving blinded study treatment may cross over to open-label selinexor, or 2) patients in the selinexor arm who have PD but may derive benefit from continued treatment with selinexor may elect to continue selinexor, but as open-label treatment (see Section [7.2.4](#)).

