14.3.4.2.2. Phase 3 Secondary Key and Efficacy Endpoint Analysis

Secondary Key Endpoint Analysis

Key secondary variables will include the following, assessed in hierarchical fashion in the order presented (to preserve the overall Type I error for the study), according to the definitions described in the objectives and study endpoints:

- OS for non-inferiority
- OS for superiority

OS endpoints will be analyzed using the stratified log-rank test as described above. In sensitivity analysis for OS, the 2-stage estimation method will be implemented to assess the impact of cross-over on the effect of selinexor on OS ([Latimer 2017](#), [Latimer 2018](#)).

Secondary Efficacy Endpoint Analysis

The comparison of TTP in the current study to TTP on the most recent prior therapy will be performed as time-to-event using a stratified log-rank test stratified by patient IDs to account for correlation within patient and adjusted for treatment arm. Note that TTP for the current study may represent censored results, therefore, to minimize the impact of censoring, this analysis may require maturation of the TTP data beyond the required time at which the number of events for the primary PFS analysis at the end of Phase 3 have occurred.

Comparison of ORR between the two treatment arms will be performed using the Cochran-Mantel-Haenszel (CMH) χ^2 or exact test as appropriate, stratified by the randomization stratification factors. For OS, an additional descriptive comparison of the median OS from the randomized selinexor arm will be made to historical OS to the extent feasible, to assist in providing the proper context for the ITT analysis of selinexor versus placebo.

[figure not shown]
DOT and PFS according to the Investigator will be analyzed using the stratified log rank test as described above.

QoL Analysis

[figure not shown]
The QoL endpoint as assessed by the EORTC QLQ-C30 and EuroQoL EQ-5D-5L questionnaires will be analyzed as a total score, using a linear mixed effects model with fixed effect of treatment arm, randomization stratification factors, and the baseline value for the parameter in the model as a covariate, as well as random effect of subjects and repeated measures over time points. For EORTC QLQ-C30 the transformed score will be used, calculated according to the *EORTC QLQ-C30 Scoring Manual*. For the EuroQoL EQ-5D-5L questionnaire, the overall health score will be used.

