4.2.2.4. ORR

ORR is defined as the proportion of patients who achieve an ICR-determined best overall response of PR or CR per RECIST v.1.1, before ICR-confirmed PD or initiating a new antineoplastic therapy. Open-label selinexor is considered a new antineoplastic therapy for the purpose of assessing ORR for blinded study treatment.

The number and percentage of patients achieving PR or CR will be summarized by treatment arm among Ph3-ITT and Ph2-ITT populations respectively.

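### The protocol tests duration of response between arms by log-rank although only responders have a duration, so the test is not a randomised comparison, and no readable SAP text replaces it

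*Protocol*

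**What the plan says.** Protocol 14.3.4.2 (Phase 3) says "Stratified log-rank tests will be used to compare the distributions of time-to-event endpoints (PFS, OS, DOR, TTP) between the two arms". The level is 0.025, one-sided. On the strata it adds: "Stratification factors for the stratified log-rank test are those that were used for randomization". Protocol 7.7 says that "randomization will be performed within each of the following 8 strata".

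Protocol 7.5.2.2 gives the definition: "DOR, defined as the time from first occurrence of CR or PR until the first date of PD", or death. A patient who never responds has no value.

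Two other places extend the rule:

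- Protocol 14.3.4.2.2: "DOT and PFS according to the Investigator will be analyzed using the stratified log rank test as described above". DOT is not defined anywhere and is probably a misprint of DOR.
- Protocol 14.3.4.1 lists DOR among the Phase 2 secondary variables and then states: "Secondary time-to-event endpoints will be analyzed using the stratified log-rank test as described above".

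In the SAP, section 1.2.2.2 keeps DOR as support for ORR. The headings under 4.2.2 are TTP, QLQ-C30, EQ-5D-5L, ORR and TTNT; DOR has none. Section 4.2.2.4 deals with response counts only: "The number and percentage of patients achieving PR or CR will be summarized by treatment arm". The general rule in 4.2 prescribes a stratified log-rank test and a stratified Cox model for secondary time-to-event endpoints and makes no exception for DOR. The readable part of section 1.7, which lists changes to the protocol's statistical section, does not mention DOR.

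**The concern.** Randomisation balances everyone assigned to the arms. It does not balance those who later respond. If selinexor produces responses in patients who would not have responded on placebo, the selinexor responders are a different kind of patient from the placebo responders. A log-rank test between the two groups then mixes any effect on duration with the difference in who responded. A drug that adds short responses can look worse, and the bias can also run the other way.

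At stake is a nominal p-value, possibly with a hazard ratio, that a reader of the study report could take as a treatment effect on durability. If placebo responders are very few, there is a separate practical problem: the stratified statistic may not exist, and the plan does not say what would then be reported.

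**Working it through.** **1. Is the comparison randomised?** This needs no assumed figure. Protocol 14.3.4.2 compares DOR between arms, and 7.5.2.2 gives DOR to responders only. Protocol 14.3.7 censors patients with no efficacy evaluations at time 0. That adds nothing to a log-rank risk set and does not bring non-responders into the test. The comparison is conditional on response, which is measured after randomisation.

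**2. How can it mislead? (assumed figures)** Let 5% of patients respond in either arm, with mean DOR 12 months, and let a further 10% respond only on selinexor, with mean DOR 6 months.

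- Responders only: selinexor (0.05 × 12 + 0.10 × 6) / 0.15 = 8 months; placebo 12 months.
- All randomised, non-responders counted as 0: selinexor 0.05 × 12 + 0.10 × 6 = 1.2 months; placebo 0.05 × 12 = 0.6 months.

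The two summaries point in opposite directions although no patient's response was shortened. In 4,000 simulated trials of this case (190 vs 95 patients, exponential durations, unstratified test), the responder-only log-rank statistic leaned against selinexor: mean Z 0.62, beyond 1.96 against it in 9% of runs and for it in 1.6%.

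**3. Can the stratified test be computed?** The plan gives no event count or power for DOR, so there is no figure of its own to reproduce. SAP 1.1 gives 285 Phase 3 patients at 2:1, so about 190 and 95 (285 × 2/3 and 285 / 3; the actual split is not stated). Response rates are not readable for either arm and are assumed below.

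The chance of no placebo responder is (1 − p)^95:

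| Placebo ORR | 0.5% | 1% | 2% | 3% | 5% |
|---|---|---|---|---|---|
| No responder among 95 | 62% | 39% (38.5%) | 15% | 5.5% | 0.8% |

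The stratified statistic needs at least one stratum with a responder in each arm. Take eight equal strata with patients falling into them at random. If the placebo responders occupy j strata, the chance that no selinexor responder falls in any of them is (1 − pS × j/8)^190, where pS is the selinexor ORR. Averaging over the number of placebo responders and over j gives the chance of no usable stratum. For 3% vs 1%, with 0, 1, 2, 3 and 4 placebo responders: 0.385 × 1 + 0.369 × 0.490 + 0.175 × 0.271 + 0.055 × 0.163 + 0.013 × 0.104 = 0.62.

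| Selinexor / placebo ORR | Not computable |
|---|---|
| 3% / 0% | 100% |
| 2% / 0.5% | 84% |
| 2% / 1% | 71% |
| 3% / 1% | 62% |
| 5% / 1% | 52% |
| 5% / 2% | 28% |
| 10% / 2% | 18% |
| 5% / 5% | 5% |
| 10% / 5% | 1% |
| 20% / 10% | about 0% |

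Simulation with equal strata agrees to within rounding, and an unequal split moved the figures by at most 6 percentage points. The condition is necessary but not sufficient, because an event must also occur while both arms are at risk. The figures are therefore slightly low.

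**4. What would a computable test show?** Power for a hazard ratio of 0.5 with d DOR events split 2:1 is Φ(0.693 × √(d × 2/9) − 1.96). This gives 11%, 18% and 31% for d = 5, 10 and 20. With placebo ORR of 0.5-2%, only 9-29% of responders on average would lie in strata that contribute (equal strata).

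**The case against.** The strongest reply is that nothing depends on this test. DOR is outside the sequence of PFS, OS non-inferiority and OS superiority (SAP 4.2.1 and 4.4), carries no alpha, and is described as support for ORR. That stands, and it limits the weight of the point.

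A second reply is that the SAP has in effect dropped the test, since DOR has no heading under 4.2.2. That is possible, but the SAP does not say so. Section 4.2 contains no exception, and readable 1.7 records no withdrawal. SAP 4.3 is redacted and might hold text on DOR, although it covers exploratory endpoints and DOR is not labelled as one. The caution in 4.2 about nominal secondary p-values is given for multiplicity, not for selection of responders.

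Two stronger readings are tempting, and the documents do not support them.

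- A reader might infer that the test will often be impossible to compute. That rests on response rates the documents do not give. Protocol section 5 cites stable disease in 30 of 52 patients as the Phase 1 signal, but it refers to section 4.3.1, which is redacted, so silence on responses there is weak evidence.
- A reader might infer that a p-value and hazard ratio for DOR will certainly be reported. Protocol 14.3.4.2 specifies a log-rank test for DOR, not a hazard ratio. The hazard ratio comes only from a SAP preamble that does not name DOR and speaks of nominal p-values conditionally.

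The two harms also do not add up: where the statistic does not exist, no misleading p-value can appear.

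**Conclusion.** The rule is wrong as written. The protocol specifies a between-arm test on subsets chosen by a post-randomisation outcome, in Phase 3 and Phase 2, and the readable SAP neither exempts DOR nor replaces the test. This conclusion needs no assumption about response rates.

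Non-computability is conditional. Across the pairs tabulated, the chance is 18-100% at an assumed placebo ORR of 0-2%, and 5% or less at 5% or above. A placebo control makes the low range plausible but does not establish it.

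The importance is minor. Sample size, alpha and every primary or key secondary conclusion are unaffected. The gain is that the study report does not carry a comparison with no causal reading.

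**What to change.** Make the change in the SAP:

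- In 4.2.2.4, state that DOR is reported descriptively among responders by arm (number of responders, Kaplan-Meier estimate, range), with no between-arm p-value or hazard ratio, in both Phase 3 and Phase 2.
- In 4.2, exempt DOR from the log-rank and Cox rule.
- In 1.7, record the departure from Protocol 14.3.4.2, 14.3.4.2.2 and 14.3.4.1, and say whether DOT means DOR.
- If a comparison of durability is wanted, use mean time in response over all Ph3-ITT patients, with non-responders counted as 0.

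The cost is a short paragraph and two one-line entries; the optional comparison would need its own brief specification. Data collection does not change. Editing the protocol list instead would need a written amendment with IRB/IEC approval, and health authority approval where required (Protocol 16.9), after enrolment has ended. The SAP route is lighter and sufficient.
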